7.1.6 Recording of Adverse Events

Medical conditions or diseases present before a subject starts study treatment are only considered AEs if they worsen after the start of the study treatment.

Adverse events may be spontaneously reported or elicited at each study visit through open-ended questioning, examination, or evaluation of a subject. To prevent reporting bias, subjects should not be questioned regarding the specific occurrence of one or more AEs.

The Investigator will record all AEs in the eCRF. Where a diagnosis is possible, it is preferable to report the diagnosis rather than a series of terms (signs/symptoms) relating to the diagnosis. If a definitive diagnosis is not possible, the individual symptoms and signs should be recorded.

The following information must be captured for all AEs:

- Onset and end date
- Severity
- Seriousness
- Relationship to EYP-1901, sham, the injection device, or the procedure
- Action taken
- Any treatment required
- Outcome

If treatment for the AE was administered, it should be recorded on the appropriate concomitant medication/procedure eCRF page. Each distinct AE should be recorded separately.

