- d. Check central retinal artery perfusion following study injection.
- e. At Day 1: measure IOP at 10 (+/- 5) and 60 (+/- 10) minutes following the EYP-1901 dose/sham injection. If IOP measurements at any study time points are 30 mmHg or higher, two additional measurements should be performed and IOP recorded as a mean of three measurements.
- f. All CFP images will be assessed by the CRC to determine the ETDRS-DRSS scores.
- g. Spectral-domain – optical coherence tomography angiography (SD-OCTA) or swept-source – optical coherence tomography angiography (SS-OCTA) imaging to be collected at these time points at pre-specified study sites where SD-OCTA equipment is available.
- h. Clinical laboratory testing will include HbA1c, hematology, serum chemistry, coagulation, and urinalysis evaluations (refer to the study Laboratory Manual).
- i. Documented HbA1c test results dated 60 days prior to the Screening Visit will be accepted.
- j. Females of childbearing potential only. Positive urine pregnancy results will be confirmed by a serum pregnancy test.
- k. Pharmacokinetic analyses of vorolanib and X-297, its main metabolite, will be performed on blood plasma samples.
- l. Adverse events, ocular and non-ocular, will be collected from the time the informed consent is signed. However, for safety analysis, only treatment-emergent adverse events (TEAEs) will be summarized.

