5.1.1 Day -30 to Day -5 (Screening Visit)

The following procedures must be completed during the initial Screening Visit ([Table 5–1](#)):

Informed Consent: Properly executed informed consent (written and verbal) is to be obtained prior to completion of any trial related procedures. A subject may take as long as needed to review the informed consent form (ICF) and consider trial participation; they may take the document with them and return at a later date (provided the study is still open for enrollment). The subject must review, sign and date the document, and receive a copy.

Inclusion/Exclusion Criteria: Inclusion/exclusion criteria ([Section 4.1](#) and [Section 4.2](#), respectively) will be reviewed to determine the subject's eligibility to participate in the trial with the Investigator verifying enrollment eligibility.

Demography, Medical History, and Medication History: Demography, complete medical history, and recent (previous 30 days) medications ([Section 6.6.1](#)) are to be recorded. Current contact lens use or ocular trauma in the study eye must be documented.

Ocular procedures to be performed with data collected for both eyes:

- ETDRS BCVA ([Appendix 1](#))
- Ocular examination – dilated ophthalmoscopy, IOP, and slit lamp biomicroscopy ([Appendix 2](#))
- CFP
- Wide-field FA
- SD-OCT assessment
- SD-OCTA assessment (at pre-specified study sites where equipment is available)

Non-ocular procedures to be performed:

- Vital sign measurements ([Section 7.3](#))
- ECG ([Section 7.4](#))
- Collect blood and urine samples for clinical laboratory evaluations ([Section 7.2](#))
- Documented HbA1c $\leq 12\%$ for Inclusion Criterion #1 (confirmed by laboratory evaluation at the Screening Visit or by a documented laboratory report dated within 60 days prior to the Screening Visit).
- Urine pregnancy test (females of childbearing potential only)
- Use of concomitant medications ([Section 7.5](#))
- Adverse events, which will be collected from the time the ICF is signed ([Section 7.1](#))

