6.5 Anaphylaxis, Overdose, and Dose Modification

Vorolanib and the inactive ingredients of EYP-1901 are not known to cause hypersensitivity reactions.

Since EYP-1901 is delivered through a pre-loaded applicator, the risk of accidental overdose is minimal. Refer to the current IB for information on potential risks associated with EYP-1901. Dose modification is not applicable since EYP-1901 is for single-delivery only.

Note: Hypersensitivity reactions to iodine and/or fluorescein used during ocular assessments are also possible.

Signs and symptoms of hypersensitivity include:

- Localized or generalized itching
- Facial flushing, generalized flushing
- Shortness of breath, wheezing
- Uneasiness and agitation
- Local edema followed by facial edema
- Light-headedness/dizziness
- Chest tightness
- Tachycardia
- Hypotension
- Rigors (chills)

If anaphylaxis occurs, the subject should be managed according to standard cardiopulmonary resuscitation (CPR) procedures, as necessary. The subject may require the following treatment:

- Epinephrine (adrenaline) to reduce the allergic response
- Oxygen
- Intravenous antihistamines and cortisone to reduce airway inflammation and improve breathing
- A beta-agonist (such as albuterol) to relieve breathing symptoms

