7.1 Adverse Events

The following are specific definitions of terms guided by the International Council for Harmonization of Technical Requirements for Pharmaceuticals for Human Use (ICH E2), Guidelines for Good Clinical Practice (GCP), and the US Code of Federal Regulations (CFR) that apply to the following sections. The severity of AEs will be graded by CTCAE version 5 or higher ([Appendix 4](#)).

Definition of Adverse Event:

An AE is defined as any new untoward medical occurrence or worsening of a pre-existing medical condition in a patient or clinical investigation subject administered an investigational or marketed (medicinal) product and that does not necessarily have a causal relationship with the product. An AE can therefore be any unfavorable and unintended sign (including an abnormal laboratory finding, for example), symptom, or disease temporally associated with the use of a medicinal product, whether or not considered related to the product.

AEs may also include pre- or post-treatment complications that occur as a result of protocol-specified procedures (eg, invasive procedures such as venipuncture, delivery procedure, etc.). Pre-existing conditions that increase in severity or change in nature during (or as a consequence of use of a medicinal product) the study will also be considered AEs.

An AE Will Not Include:

- Medical or surgical procedures (eg, surgery, endoscopy, tooth extraction, transfusion) for events that led to the procedure
- Pre-existing diseases, conditions, or laboratory abnormalities present or detected prior to the Screening Visit, unless they worsen during the study
- Situations where an AE or untoward medical occurrence has not occurred (eg, hospitalization for elective surgery, social and/or convenience admissions)

Associated with the Use of the Drug (Causality):

There is a reasonable possibility that the event may have been caused by the study medicinal product (and/or the administration procedures).

Unexpected Adverse Event:

Any event that is not identified in nature, severity, or frequency in the current version of the IB; or in the product labeling for marketed products. For example, if the IB or product labeling referred to elevated hepatic enzymes or hepatitis, then an event of hepatic necrosis would be considered unexpected by the virtue of the greater severity. The Sponsor or designee will determine AE expectedness.

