7.1.7 Adverse Event Reporting

All subjects enrolled in the study will be evaluated for AEs, which will be collected from the time the ICF is signed until study completion ([Table 5-1](#)).

All AEs will be evaluated from onset until resolution or stabilization, whichever is first. Adverse events that continue after the subject's discontinuation or completion of the study will be followed until their medical outcomes are determined or until no further change in the condition is expected. The event and outcome will be reported in writing by the Investigator to the Sponsor. The Investigator shall supply the Sponsor and Institutional Review Board (IRB)/Ethics Committee (EC) with any additional requested information, notably for reported deaths.

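### Protocol Section 7.1.6 does not count a condition that arises between consent and dosing as an AE unless it worsens after dosing, while 7.1, 7.1.7, 5.1.1 and Table 5-1 count it, so pre-dose AE and SAE recording depends on the section a site follows.

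*Protocol*

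**What the plan says.** Protocol Section 7.1.6, on recording: "Medical conditions or diseases present before a subject starts study treatment are only considered AEs if they worsen after the start" of study treatment. Its reference point is the Day 1 injection.

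Other parts of the protocol use an earlier point:

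- Section 7.1, in its list of what is not an AE: "Pre-existing diseases, conditions, or laboratory abnormalities present or detected prior to the Screening Visit, unless they worsen during the study". The reference point is the Screening Visit.
- Section 7.1, in the AE definition: "AEs may also include pre- or post-treatment complications that occur as a result of protocol-specified procedures". AEs can therefore precede treatment.
- Section 7.1.7, on AEs: "which will be collected from the time the ICF is signed until study completion".
- Section 5.1.1, among the Screening Visit procedures: "Adverse events, which will be collected from the time the ICF is signed".
- Table 5-1 footnote l: "Adverse events, ocular and non-ocular, will be collected from the time the informed consent is signed". The footnote then limits the safety summaries to TEAEs.

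Section 7.1.2 defines an SAE as an AE with one of the listed outcomes. Section 7.1.7.1 requires every SAE, whatever its cause, to reach the Sponsor within 24 hours of the Investigator's first awareness.

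Treatment emergence is defined twice. Protocol Section 11.4.7 counts events that start after dosing and also events already present that worsen after it. SAP Section 11.1 counts only AEs whose start is on or after the treatment date and does not mention worsening.

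**The concern.** Footnote l keeps two ideas apart: AEs are collected from consent, and a subset of them, the TEAEs, is summarized. Section 7.1.6 blurs this, because it applies a treatment-start test to whether something is an AE at all. It also stands in the section on recording AEs, where site staff would look.

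The main stake is serious events before dosing. Take a subject who develops a new cardiac condition after screening and is admitted to hospital. Under 7.1 and 7.1.7 this is an AE, hence an SAE with a 24-hour report. Under 7.1.6 a site could enter it as history and report nothing. With about 30 sites, different readings are likely, and the AE and SAE listings would then mix two recording practices.

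**Working it through.** There is no figure in the plan to reproduce, and the point rests on no sample size or event count. The check is a comparison of the rules, plus the length of the interval they disagree about.

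**Interval.** Screening runs from Day -30 to Day -5 (Table 5-1). Dosing is on Day 1, and there is no Day 0 (SAP Section 8.2).

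- Latest screening: from Day -5 to Day 1 is 5 + 1 - 1 = 5 days.
- Earliest screening: from Day -30 to Day 1 is 30 + 1 - 1 = 30 days.

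This agrees with the 5 to 30 days in protocol Section 3.4. The interval is slightly longer if consent is signed before the Screening Visit.

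**Three courses of an event, each starting after consent and screening and before dosing.**

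| Course | 7.1, 7.1.7, 5.1.1, footnote l | 7.1.6 | TEAE, protocol 11.4.7 | TEAE, SAP 11.1 |
|---|---|---|---|---|
| A. Persists, does not worsen | AE | Not an AE | No | No |
| B. Persists, worsens after dosing | AE, onset before dosing | AE once it worsens | Yes | Depends on the recorded onset |
| C. Resolves before dosing | AE | Not naturally covered | No | No |

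*Course A* is the direct conflict. The condition does not predate screening, so 7.1 does not exclude it, and three places collect it. It is present before treatment and does not worsen, so 7.1.6 says it is not an AE. SAE status follows AE status (7.1.2), so the duty in 7.1.7.1 is equally undecided. Section 7.1.1 adds to the clash: a fall of at least 15 letters from the previous visual acuity measurement is an AE, and acuity is measured at both Screening and Day 1. A fall between those visits caused by new disease is an AE by that list, while 7.1.6 says the disease is not.

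*Course A in the outputs.* It is not a TEAE under either definition, so it enters no TEAE table. It does belong in the listings of all AEs and of SAEs that SAP 11.1 plans, and it appears there or not according to the rule the site used.

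*Course B* is an AE under both rules. Under 11.4.7 it is a TEAE whatever onset date is recorded. Under SAP 11.1 it is a TEAE only if the recorded start is on or after dosing. With a pre-dose onset and no new record for the worsening, it is left out. A consent cut-off makes the pre-dose onset the normal entry, so that change on its own could remove Course B events from the TEAE tables.

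**The case against.** The strongest reply is that 7.1.6 sets no start for AE collection. It is one sentence about pre-existing conditions, whereas the collection start is given three times, always as consent, and Table 5-1 marks AEs at Screening. A site that follows the schedule will collect from consent. This stands as a limit: it would be wrong to say that 7.1.6 starts AE collection at dosing. It does not remove the conflict, because the sentence still says which conditions count as AEs, and Course A gets opposite answers.

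The general definition in 7.1 also speaks of subjects who have been given a product, so 7.1 is not wholly on the consent side. That is fair, but the same section admits pre-treatment complications and sets its exclusion at screening.

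Three stronger readings are tempting, and the documents do not support them.

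- *Reactions to screening angiography are lost.* Section 6.5 says "Hypersensitivity reactions to iodine and/or fluorescein used during ocular assessments are also possible", and fluorescein angiography is done at screening. But 7.1 expressly makes procedure complications before treatment AEs, and a reaction that has resolved by Day 1 is not naturally a condition present when treatment starts.
- *The conflict by itself makes TEAE counts differ between sites.* Under protocol 11.4.7 it does not, because worsening counts. The difference arises only through SAP 11.1, which is a separate mismatch.
- *A number of subjects, or 5 percentage points per subject in an arm of 20, is at stake.* The documents give no AE rate for the screening period. Events that stay pre-dose enter no arm percentage, since only TEAEs are summarized.

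**Conclusion.** The conflict is real and is in the current text. A condition that arises after consent and screening, is still present at dosing and does not worsen is an AE, and if serious a 24-hour SAE, under 7.1, 7.1.7, 5.1.1 and Table 5-1 footnote l. Under 7.1.6 it is neither. The window is 5 to 30 days per subject.

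The reach is limited to pre-dose AE recording, the all-AE and SAE listings, and SAE reporting. The primary endpoint, the other efficacy analyses and the arm percentages are unaffected. How many subjects are involved cannot be estimated from the documents. The conclusion assumes that 7.1.6 is applied as written; a site that treats it as subordinate to 7.1.7 would record such events correctly.

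The SAP 11.1 definition is a linked but separate mismatch. It has to be settled in the same change, because moving the cut-off alone would make it matter more.

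**What to change.** Reconcile the sections to one cut-off.

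1. In protocol 7.1.6, replace both references to the start of study treatment with the signing of informed consent: a condition present before consent is an AE only if it worsens after consent.
2. In the 7.1 list of what is not an AE, use consent in place of the Screening Visit. This also closes the small gap between 7.1 and 7.1.7 when consent is signed before that visit.
3. Bring the TEAE definition in SAP 11.1 into line with protocol 11.4.7 by adding events present before dosing that worsen after it. Alternatively, require post-dose worsening to be entered as a new AE record with its own onset date.
4. Put the recording rule in the eCRF completion guide.

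Events between consent and dosing are then always AEs, with SAE reporting under 7.1.7.1, and treatment emergence remains an analysis rule. The cost is two sentences of protocol wording, one SAP sentence or recording instruction, and a short note to sites. The downside is a few more pre-dose AE records.

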7.1.7 Adverse Event Reporting

All subjects enrolled in the study will be evaluated for AEs, which will be collected from the time the ICF is signed until study completion ([Table 5-1](#)).

All AEs will be evaluated from onset until resolution or stabilization, whichever is first. Adverse events that continue after the subject's discontinuation or completion of the study will be followed until their medical outcomes are determined or until no further change in the condition is expected. The event and outcome will be reported in writing by the Investigator to the Sponsor. The Investigator shall supply the Sponsor and Institutional Review Board (IRB)/Ethics Committee (EC) with any additional requested information, notably for reported deaths.

7.1.7.1 Reporting of Serious Adverse Events

All SAEs, regardless of cause(s) or relationship to study drugs, must be recorded on the appropriate eCRF page and reported to the Sponsor within 24 hours of the Investigator's first awareness using the study's designated SAE/SADR (Serious Adverse Drug Reaction) Report Form.

Minimal information to be provided on the SAE/SADR Report Form includes:

- Protocol number
- Site and Investigator identifiers

- Subject number
- Brief description of the event(s)
- Onset date of the event
- Outcome of the event as of the date of report, if known
- Resolution date and time, if the event(s) resolved
- Any medication administered to treat the event
- Investigator's assessment of the causal relationship of the SAE to the study medicinal product
- Additional and follow-up information as requested by Sponsor or its designee

SAEs must be reported using the study's designated SAE/SADR Report Form and sent to:

PPD [REDACTED]
[REDACTED]
[REDACTED]

The Investigator will also compile other relevant documentation with urgent priority (eg, copies of test results, hospital discharge summary, autopsy report, etc.), and send this information to the Sponsor (or Sponsor's designee).

The FDA and all participating Investigators shall be notified by a written Investigational New Drug Application (IND) safety report of any AE associated with the use of the investigational product that is both serious and unexpected no later than 15 calendar days from the Sponsor's awareness date of the event. An SAE is considered to be associated with the use of the investigational product if the relationship between the SAE and the investigational product is classified by the Investigator as "possibly related" or "probably related" (ie, suspected, unexpected serious adverse reaction [SUSAR]). Any unexpected fatal or life-threatening SAE associated with the use of the investigational product will be reported to the FDA by the Sponsor within 7 calendar days.

The IRB/EC should be notified of SAEs as required in accordance with the local institutional policy.

All Investigators participating in the study will be notified of unexpected SAEs determined to be related to study treatment/injection procedure.

Pregnancy

Pregnancy that occurs during the study must be immediately reported to the Investigator who will immediately notify the Sponsor or designee within 24 hours of first awareness using the study's designated Pregnancy Report Form. This includes any pregnancy following maternal or paternal exposure to the study treatments.

The pregnancy should be followed to term. The outcome, including premature termination must also be reported to the Sponsor or designee within 24 hours of the Investigator's awareness using the Pregnancy Report Form. All live births must be followed for a minimum of 4 weeks or to the first well-baby visit. All reports of congenital abnormalities/birth defects and spontaneous abortions/miscarriages should be reported as SAEs. Elective abortion procedures without complications should not be considered as AEs.

If the Investigator becomes aware of a pregnancy occurring in any male subject's partner during the male subject's treatment with the assigned study medicinal product, the Investigator must submit this information to the Sponsor on the Pregnancy Report Form.

The Pregnancy Report Form should be sent to:

PPD [REDACTED]
[REDACTED]
[REDACTED]

Special Situations

Notification must be made to the Sponsor or designee of any special situation which includes the following, regardless of any associated AE:

- A medication error, defined as any unintentional error in the prescribing, dispensing, or administration of a medicinal product while in the control of the health care provider or subject.
- Abuse, defined as persistent or sporadic intentional excessive use of a medicinal or other product.
- Misuse, defined as any intentional or inappropriate use of a medicinal product that is not in accordance with the protocol instructions or local prescribing information.
- An overdose, defined as an accidental or intentional administration of a quantity of a medicinal product given per administration or cumulatively which is above the maximum recommended dose per protocol or in the product labeling. In cases of a discrepancy in drug accountability, overdose will be determined only when it is clear that the subject received an excess dose(s).

Special situations should be reported on the study's designated SAE/SADR Report Form except pregnancies for which there is a dedicated form. If any special situation results in clinical sequela(ae)/AE(s), the event(s) must be recorded on the AE eCRF. If the AE is serious, the SAE eCRF must be completed and a SAE/SADR Report Form must be completed and submitted to the Sponsor or designee within 24 hours of first awareness.

Special situations involving concomitant medication do not need to be reported on the SAE/SADR Report Form. However, special situations involving concomitant medication that result in clinical sequelae/AEs should be reported on the AE eCRF. In addition, any inappropriate use of prohibited concomitant medications should not be reported as "misuse" but may be more appropriately documented as a protocol deviation.

Using the SAE/SADR Report Form, reports of special situations should be sent to:

PPD [REDACTED]
[REDACTED]
[REDACTED]

7.2 Clinical Laboratory Evaluations

The clinical laboratory tests listed in the Study Laboratory Manual, including hematology, HbA1c, serum chemistry, coagulation, and urinalysis, will be done at the study visits indicated in [Table 5-1](#).

A central laboratory will be used to measure laboratory parameters. The Investigator will use these results for clinical purposes and the laboratory data will be used for safety analyses. Normal value ranges and laboratory certification will be collected prior to study initiation.

Investigators must review and document laboratory test results, as well as address the clinical significance and causality (for significant abnormalities). Clinically significant abnormal laboratory results should be repeated as soon as possible. [Section 7.1.4](#) provides further guidance as to when abnormal laboratory results are to be reported as AEs.

